1.2 JUSTIFICATION OF THE STUDY AND OF THE STUDY DESIGN

1.2.1 Justification of selecting patients with hematological malignancies

Hematological malignancies are heterogeneous diseases. There is increasing evidence in preclinical models that brd inhibition can lead to anti tumor activity against various illnesses from acute leukemia [*Redner 1999; Zuber 2011; Dawson 2011; Blobel 2011*] to lymphoma [*OTX015 Investigator's Brochure*]. and myeloma [*Delmore 2011*] [*OTX015 Investigator's Brochure*]. It is known that in many hematological malignancies, the oncogenesis is driven by the oncogene c-Myc [*Boxer 2001 ; Vita & Henriksson 2006; Mertz 2011; Delmore 2011 ; Cuccuini 2012*]. It has been shown that brd inhibition was frequently associated with c-Myc, and downstream targets downregulation [*Mertz 2011*].

Though a significant proportion of patients with acute leukemia and lymphoma can be cured or can benefit of prolonged overall survival with current therapies, the majority of patients with hematological malignancies will die from their disease. The level of unmet medical need is therefore very high and innovative new drugs are eagerly expected.

1.2.2 Justification of the new drug product formulation

The drug product formulation used in the healthy volunteer studies was designed to deliver the active agent to the lower intestine for treatment of inflammatory bowel disease. For treatment of cancer, it is desirable for have a formulation that achieves the highest possible systemic levels of active agent. A bioavailability study in dogs comparing the clinical formulation used for the healthy volunteer studies (Eudragit; microcrystalline cellulose spheres coated with an ethanolic solution of OTX015, triethyl citrate, aminoalky methacrylate copolymer RS, and methacrylic acid copolymer, spray dried and mixed with talc, magnesium aluminometasilicate, and light anhydrous silicic acid) and the formulation used for nonclinical safety studies (25% OTX015:PVP in ethanol, spray dried and mixed with lactose, corn starch, crystalline cellulose, and carmellose calcium) found 16%-17% bioavailability (mean C_{max} of 211 ng/mL and mean AUC_{0-24h} of 833 ng•h/mL at 3 mg/kg) for the clinical formulation compared with 30%-40% bioavailability (mean C_{max} of 414 ng/mL and mean AUC_{0-24h} of 1787 ng•h/mL at 3 mg/kg) for the nonclinical formulation. The 2-fold higher systemic exposure achieved with the solid dispersion OTX015:PVP formulation used
in nonclinical safety studies compared with the formulation used in the healthy volunteer studies was consistent with the design of the clinical formulation.

Although the solid dispersion OTX015:PVP formulation achieved adequate systemic exposure, polyvinyl pyrrolidone (PVP) is hygroscopic, so screening was performed to identify an alternative excipient for a solid dispersion formulation for clinical studies in cancer patients. A bioavailability study in dogs of the solid dispersion OTX015:PVP formulation used in nonclinical safety studies and the solid dispersion OTX015:HPMCAS-MG formulation to be used in the clinical studies in cancer patients found comparable (not statistically different) bioavailability for both the PVP solid dispersion (mean C_{max} of 487 ng/mL and mean AUC_{0-24h} of 1555 ng•h/mL at 3 mg/kg) and the HPCMAS solid dispersion (mean C_{max} of 371 ng/mL and mean AUC_{0-24h} of 1970 ng•h/mL at 3 mg/kg). Accelerated stability studies have confirmed that the solid dispersion PVP formulation absorbs some moisture, while the solid dispersion HPMCAS formulation does not.

1.2.3 Justification of the starting dose

Traditionally, for first-in-human oncology trials in patients with advanced and/or metastatic disease the starting dose is calculated based on the maximally tolerated dose (MTD) or highest non-severely toxic dose (HNSTD) in the most sensitive species in 28-day repeated dose toxicology studies [CHMP/SWP/997/96; Senderowitz 2010]. In the case where rodents are the most sensitive species, the starting dose in humans is one-tenth the rodent MTD or LD_{10} . In the case where dogs are the most sensitive species, the starting dose in humans is one-sixth the dog HNSTD or MTD. In 28-day repeated dose toxicity studies of OTX015, the MTD in rats was 30 mg/kg/day, corresponding to a mean Day 28 AUC_{0-24h} of 6715 ng•h/mL, and the HNSTD in dogs was 10 mg/kg/day, corresponding to a mean Day 28 AUC_{0-24h} of 4377 ng•h/mL. Based on the MTD in rats and using a conversion factor of 6 from mg/kg to mg/m² in rats and assuming a mean BSA of 1.5 m² for humans, the starting dose is calculated as 27 mg [i.e., $(30 \times 6 \times 1.5)/10$]. Based on the HNSTD in dogs and using a conversion factor of 20 from mg/kg to mg/m² in dogs and assuming a mean BSA of 1.5 m^2 for humans, the starting dose is calculated as 50 mg [i.e., (10 x 20 x 1.5)/6]. The most conservative estimate, based on the MTD in rats, gives a starting dose of 27 mg in humans. As noted above, the bioavailabilites in dogs found for the solid dispersion OTX015:PVP formulation used in nonclinical safety studies and the solid dispersion OTX015:HPMCAS formulation to be used in clinical studies in cancer patients were not statistically different, so a starting dose of 27 mg can be justified.

However, a starting dose of 10 mg will be used, based on the following considerations: (1) in the healthy volunteer studies, a dose of 40 mg/day over 10 consecutive days was well tolerated, with no severe AEs or dose-limiting toxicities; (2) patients with advanced hematologic malignancies may tolerate treatment less well than healthy volunteers, justifying a starting dose one level below the highest repeated dose administered to healthy volunteers, or 20 mg/day, and (3) the systemic bioavailability in dogs of the formulation to be used in studies in cancer patients is 2-fold higher than the formulation used in healthy volunteers, so a dose of 10 mg/day using the new formulation is expected to give a systemic exposure comparable to the dose of 20 mg/day using the formulation in the healthy volunteer study.

The information in this document is the property of OncoEthix and is confidential. Neither the document nor the information contained therein may be reproduced or disclosed outside OncoEthix without their written consent

1.2.4 Justification of the schedule of administration and of various schedules according to the treated condition

In vitro experiments of OTX015 against lymphoma and leukemia cells have shown that c-Myc downregulation and anti-proliferative effect were reversible after washout [*OTX015 Investigator's Brochure*]. Thus, a continuous exposure is deemed appropriate for an optimal antitumor effect. An intermittent schedule (14 days ON/ 7 days OFF every 21 days) was initially deemed more appropriate for the assessment of toxic effects in acute leukemia patients, known to experience many disease-related AEs. After the assessment of 3 dose levels with both an intermittent and a continuous schedule, showing the tolerance and feasibility of a continuous schedule and accumulating evidence that a continuous exposure to adequate concentrations of OTX015 is required for an optimal antitumor activity, the same continuous schedule will be finally delivered to all patients.

1.2.5 Justification of two parallel dose escalation subsets

Patients with relapsed/refractory acute leukemia usually experience severe/life-threatening AEs associated to disease-related severe bone marrow failure (especially fever, sepsis and hemorrhages) sometimes associated with metabolic disorders (hyperuricemia, hyperkalemia, hypocalcemia, renal failure, metabolic acidosis...). Thus, it is difficult to assess the relationship of treatment emergent AEs to a new medication having yet an undefined safety profile. Especially, hematological toxicities in acute leukemia cannot be assessed according to the same guidelines as other hematological malignancies, such as lymphoma or myeloma, without or with only mild/moderate bone marrow failure. Because peripheral blood cell counts (BCC) are usually extremely low at study entry in patients with acute leukemia, bone marrow toxicity cannot be assessed based upon decrease of BCC on study treatment. Hence it is not possible to pool and assess together acute leukemia and other malignancies in very small patient cohorts of 3-6 patients to assess toxicities and establish a reliable recommended dose.

Therefore, dose escalations and the safety and pharmacokinetics of OTX015 will be evaluated separately in patients with acute leukemia on one hand, and in patients with other hematological malignancies on the other hand.

1.3 CONCLUSION

OTX015 is a new innovative compound acting through Brd inhibition and epigenetic modulation of gene expression with promising anti-tumor activities in various hematological malignancies. It has been already tested in human healthy volunteers and was well tolerated at doses which achieved plasma concentration in the range of active concentration against *in vitro* tumor models. The antitumor effect is often associated with c-Myc down-regulation.

This clinical study is aimed at assessing the recommended dose (RD), the safety profile, PK and PD of OTX015 in patients with refractory/relapsed hematological malignancies, and to detect clues of clinical anti-tumor activity.

The information in this document is the property of OncoEthix and is confidential. Neither the document nor the information contained therein may be reproduced or disclosed outside OncoEthix without their written consent

2 STUDY OBJECTIVES

2.1 PRIMARY OBJECTIVE

To determine the recommended dose (RD) of OTX015/MK-8628 for further phase II studies, in patients with acute leukemia and in patients with other hematological malignancies.

2.2 SECONDARY OBJECTIVES

The secondary objectives of the study are:

- To assess the safety profile of OTX015/MK-8628 as a single agent in patients with haematological malignancies
- To assess pharmacokinetics (PK) of OTX015/MK-8628 in patients with haematological malignancies and PK/safety relationship
- To assess pharmacodynamics (PD) of OTX015/MK-8628 in patients with haematological malignancies, PD/safety and PK/PD relationships
- To detect clues of clinical antitumor activity

2.3 EXPLORATORY

• To detect predictive factors (among patient or tumor characteristics) of clinical activity

3 STUDY DESIGN, DURATION AND DATES

3.1 STUDY DESIGN

This is a multicenter, multinational dose finding, open label, phase Ib study.

3.1.1 Dose escalation part

- Two dose escalation subsets will be assessed independently in parallel: patients with acute leukemia and patients with other hematological malignancies.
- Patients will be enrolled by successive cohorts of 3 patients in each dose escalation subset.
- Three patients will be initially treated at the starting dose level (DL) in each subset. If no dose limiting toxicity (DLT) is observed among these 3 patients during the first cycle of treatment (i.e. the first 21 days following study treatment initiation, regardless of the treatment schedule), the next 3 patients will be treated at the DL immediately above, according to the dose escalation schedule defined in section 5.2.4.1. In the absence of DLT observed at the completed DL, the dose will be doubled.

- At each DL in each subset, the second patient enrolled will not start the study treatment before the first treated patient of the cohort will have completed at least 2 weeks of treatment (i.e. 14 consecutive daily administrations). The first patient enrolled in a higher DL cohort will not start the study treatment before the last treated patient in the DL immediately below will have completed at least one cycle of study treatment (i.e. 21 days following study treatment initiation, regardless of the treatment schedule)..
- If one out of 3 patients of a cohort experiences a DLT during the first cycle (i.e. 21 days following study treatment initiation, regardless of the treatment schedule), 3 additional patients will be entered at this DL. If no more than 1/6 treated and evaluable patient experience a DLT, the dose escalation will proceed to the DL immediately above. As soon as a DLT is observed, the magnitude of dose escalation will follow a Fibonacci-like model. (see section 5.2.4.1).
- If more than one patient out of 6 (or more than one out of 3) patients experiences a DLT, the DL will be considered exceeding the maximum tolerated dose (MTD) for this subset.
- Patients not evaluable for DLT are those having received less than 85% of the intended cumulative dose during the first 21 days (i.e. those receiving less than 18 days of treatment for the continuous, 21-day schedule or less than 12 days of treatment for the intermittent, 14 days ON/ 7 days OFF schedule) and who have not experienced a DLT, will be replaced.
- The dose escalation will be stopped independently in each subset upon decision of the Safety Monitoring Committee (SMC). This decision could be taken if one of the following conditions is met:
 - A DL exceeding the MTD has been reached
 - Biological activity (PD) or sustained biologically active concentrations (PK) of OTX015/MK-8628 have been achieved
 - Or any other unforeseen condition, which, in the judgment of the SMC, would prevent, or would not deserve, further dose escalation.
- In the absence of other data (PD or PK) suggesting a lower RD, the MTD will be considered the RD (one DL below the dose exceeding the MTD) in each subset. At least 6 evaluable patients will be enrolled at the supposed RD. The RD will be confirmed for each subset if no more than 1/6 patient experiences a DLT. Otherwise the DL immediately below will be explored with a minimum of 6 patients treated.

3.1.2 Expansion part

• Once the RD will be established with at least 3 patients having received at least 2 cycles of study treatment in each subset, the study will be prolonged with expansion cohorts in selected patients to confirm feasibility, safety, PK and PD at the RD. At least 12 evaluable patients with acute leukemia will be treated at the RD established for patients with acute

leukemia. At least 12 evaluable patients with lymphoma and at least 12 patients with multiple myeloma will be treated at the RD established for patients with other hematological malignancies. Additional expansion cohorts may be decided by the SMC, based upon the data collected during the dose escalation phase.

3.2 DEFINITION OF DOSE LIMITING TOXICITIES (DLTS)

DLTs are defined as any of the following treatment-related adverse events occurring in the first cycle (during the first 21 days following study treatment initiation (except hematological toxicity in AL patients confirmed at day 43, see below), regardless of the administration schedule), leading to dose modifications, study treatment interruption or discontinuation, unless a relationship to study medication can be definitely ruled out.

DLTs will be reported immediately to the sponsor using Serious Adverse Events Report Forms (SAERF) with reason for seriousness: "other important medical event" if there is no other reason for seriousness.

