The SMC will be composed of the principal investigators (PI) of each participating center, the pharmacokinetics (PK) specialist, the medical and safety representatives of the Sponsor and one independent expert in oncology/hematology phase I development. All decisions taken by the SMC and their rationale will be recorded in meeting minutes that will be integrated in the final clinical study report.

Definition of dose limiting toxicities (DLTs)

The DLTs are identical to the events leading to treatment interruption and dose adjustment (see Dose & schedule adaptation), as well as any other unforeseen drug-related AE (including liver function test abnormalities as reported in Dose and Schedule Adaptation) resulting in study drug discontinuation or interruption with/without dose reduction. But only such AEs occurring during cycle 1 (or the first 21 days following the first dosing of OTX015) are considered DLT, except the hematologic DLT for patients with acute leukemia that must be confirmed after 6 weeks of treatment,

Treatment compliance

Patients will record daily in a specific diary, the number of capsules swallowed, time of intake, as well as possible reactions, including vomiting, and their time of occurrence. At each study visit the hospital pharmacist of the study center will provide the patient with the needed number of capsules for the visit interval and retrieve the unused capsules that will be kept until study end for accountability by the study monitor.

Number of subjects

The total number of patients enrolled will depend on the number of DLs explored and of DLT encountered.

Approximately 80 evaluable patients will be enrolled in the dose escalation part (40 by subset acute leukemias/other hematological malignancies)

At least 12 evaluable patients by expansion cohorts will be enrolled in at least 3 expansion cohorts

The total number of evaluable patients is estimated to be 125.

Pharmacokinetics (PK)

Blood collection:

• Once-a-day schedule

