3.2.1 Non-hematological DLTs

- Any grade 3 or 4 non-hematological event (regardless of duration), unless it was not optimally treated with supportive care (e.g. grade 3 vomiting not adequately treated according to antiemetic standard of care).
- Grade 3-4 asymptomatic laboratory abnormal values lasting > 7 days. This definition applies for patients with lab values grade ≤ 1 at baseline. For patients with grade 2 values at baseline, only grade 4 lasting > 7 days will be considered DLT, unless the SMC considers the event clinically significant. See below for liver function tests*.
- Any prolonged grade 2 toxicity (lasting more than 2 weeks) leading to treatment interruption and/or dose reduction

* Any of the following liver test abnormalities** (see Appendix 16.12)

- ALT or $AST > 8 \times ULN$
- ALT or AST $> 5 \times ULN$ for > 2 weeks
- ALT or AST > 3 x ULN AND (total bilirubin > 2 x ULN OR INR > 1.5)
- ALT or AST > 3 x ULN with the appearance of fatigue, nausea, vomiting, right upper quadrant pain or tenderness, fever, rash and/or eosinophilia (> 5%), unless the investigator assesses the rash or fatigue to be related to OTX015 and not related to liver impairment with sponsor's agreement.

**Note: All patients with these liver test abnormalities should be monitored weekly until all abnormalities return to normal or to the baseline state. For patients with isolated total bilirubin increases >2 x ULN or 2 x baseline (if elevated at baseline), except if associated with direct bilirubin \leq ULN, monitoring should be every 2 weeks until bilirubin returns to normal or to the baseline state. Drug induced liver injury (DILI) may develop or progress even after the causative

drug has been stopped. Results should be recorded on the CRF and in the database. See guidelines on the handling of these events (potential Hy's law cases).

Investigators must be warned about qualifying fatigue/asthenia as a DLT. Grade 3 fatigue/asthenia deemed to be related to the study medication is a DLT as per protocol. However, multiple causal events, often intricate, may result in severe fatigue/asthenia in cancer patients participating to a phase I clinical trial, including disease progression, concomitant medications, concomitant medical conditions, anxiety, depression, transportation, etc.

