5.2.4.2 Dose adaptation

Study product dosing (OTX015/MK-8628) will be interrupted in the event of AEs corresponding to the definition of a DLT (see section 3.2), but regardless of the cycle in which they occur:

Non hematological toxicity

- Any grade 3 or 4 non-hematological event (regardless of duration), unless it was not optimally treated with supportive care (e.g. grade 3 vomiting not adequately treated according to antiemetic standard of care).
- Grade 3-4 asymptomatic laboratory abnormal values lasting > 7 days. This definition applies for patients with lab values grade ≤ 1 at baseline. For patients with grade 2 values at baseline, only grade 4 lasting > 7 days will be considered DLT, unless the SMC considers the event clinically significant. See below for liver function tests*.

- Any prolonged grade 2 toxicity (lasting more than 2 weeks) leading to treatment interruption and/or dose reduction.
- * Any of the following liver test abnormalities** (see Appendix 16.12)
 - ALT or $AST > 8 \times ULN$
 - ALT or AST $> 5 \times ULN$ for > 2 weeks
 - ALT or AST > 3 x ULN AND (total bilirubin > 2 x ULN OR INR > 1.5)
 - ALT or AST > 3 x ULN with the appearance of fatigue, nausea, vomiting, right upper quadrant pain or tenderness, fever, rash and/or eosinophilia (> 5%), unless the investigator assesses the rash or fatigue to be related to OTX015 and not related to liver impairment with sponsor's agreement.

**Note: All patients with these liver test abnormalities should be monitored weekly until all abnormalities return to normal or to the baseline state. For patients with isolated total bilirubin increases >2 x ULN or 2 x baseline (if elevated at baseline), except if associated with direct bilirubin \leq ULN, monitoring should be every 2 weeks until bilirubin returns to normal or to the baseline state. Drug induced liver injury (DILI) may develop or progress even after the causative drug has been stopped. Results should be recorded on the CRF and in the database. See guidelines on the handling of these events (potential Hy's law cases).

Hematological toxicity

Patients with AL

• Pancytopenia with a hypocellular bone marrow and no marrow blasts lasting for ≥ 6 weeks after the start of a cycle.

Patients with other hematological malignancies

- Any grade 3 neutropenia, with fever or infection
- Any grade 3 thrombocytopenia with bleeding,
- Any grade 4 neutropenia or thrombocytopenia, regardless of symptoms and lasting \geq 3 days.

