OTX015/MK-8628 dosing will be resumed when all toxic events have resolved to grade < 2 (or baseline value).

• At reduced dose :

- During the dose escalation, at the DL immediately below.

- During expansion cohorts, patients treated at 80mg QD (2 weeks ON/ 1 week OFF) will have their dose first reduced to 60mg QD (2 weeks ON/ 1 week OFF), then to 40mg QD (2 weeks ON/ 1 week OFF), should the same toxicity recurs.

• Dosing interruption for > 2 weeks due to toxicity will lead to definitive study treatment discontinuation, unless the investigator thinks the patient's best interest is to pursue study treatment.

• If the same DLT is observed again after dose reduction, the study treatment should be definitely discontinued, unless the investigator thinks the patient's best interest is to pursue study treatment with further dose reduction, with sponsor's agreement.

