# **12.3 PRIMARY CRITERION: DOSE LIMITING TOXICITY**

DLTs are defined as any treatment-emergent adverse events (TEAEs) occurring during the first cycle (i.e., the first 21 days following study treatment initiation; note that hypocellular bone marrow and no marrow blasts in AL patients had to be confirmed at day 43), leading to treatment interruption or dose adjustment, or any unforeseen drug-related AE leading to study treatment interruption or discontinuation, unless a relationship to study medication can be definitively ruled out.

The number of patients evaluable for DLT/with DLT in cycle 1 will be tabulated per dose level and overall for safety population.

Type of DLT will be tabulated for patients evaluable for DLT by DL and overall.

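### Two competing DLT definitions: under the one in protocol 3.2 and SAP 12.3, a listed cycle 1 toxicity with no dosing consequence can be counted as no DLT

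*Protocol*

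**What the plan says.** **Wording that needs a dosing consequence.** Protocol 3.2 covers listed treatment-related events in the first 21 days, on any schedule, "leading to dose modifications, study treatment interruption or discontinuation, unless a relationship to study medication can be definitely ruled out". SAP 12.3, the primary-criterion section, refers to cycle 1 events "leading to treatment interruption or dose adjustment, or any unforeseen drug-related AE leading to study treatment interruption or discontinuation". The two differ slightly: the protocol names discontinuation for listed events, while the SAP names it only for unforeseen ones.

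**Wording that goes by event type.** The protocol synopsis states: "The DLTs are identical to the events leading to treatment interruption and dose adjustment (see Dose & schedule adaptation". It attaches the condition of a resulting discontinuation or interruption only to other, unforeseen drug-related events. The SAP synopsis reads the same in substance. Protocol 3.2.1 says: "Grade 3 fatigue/asthenia deemed to be related to the study medication is a DLT as per protocol", with no dosing condition. In the 3.2.1 list only one item repeats the condition: "Any prolonged grade 2 toxicity (lasting more than 2 weeks) leading to treatment interruption and/or dose reduction". The list inside SAP 12.3 has the same pattern, with the condition only on its catch-all item.

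**Dosing text.** Under protocol 5.2.4.2, dosing "will be interrupted in the event of AEs corresponding to the definition of a DLT (see section 3.2), but regardless of the cycle" of onset. That section then lists the triggering events in full and provides for resumption at a reduced dose. The recommended dose (RD) schedule is days 1 to 14 of a 21-day cycle. Protocol 9 asks, as far as possible, for a single reason for discontinuation when several coincide, and gives progression with toxicity as its example.

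**The concern.** DLT is the primary endpoint and drives escalation and the RD. If a dosing change is part of the definition, scoring depends on whether a dose was due and on why treatment stopped, as well as on what happened to the patient. On a 14/21 schedule, days 15 to 21 lie inside the DLT window but no dose is planned, so there is none to withhold. A patient who has taken all 14 doses is already evaluable. If an off-week event is not scored, that patient stays in the denominator as DLT-free and is not replaced. With cohorts of 3 and 6, one such patient can change a decision: 0/3 doubles the dose, 1/3 adds three patients, and the RD is confirmed at no more than 1/6.

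**Working it through.** **1. Evaluability thresholds (protocol 3.1.1).** 85% of planned cycle 1 days:
- 14/21: 0.85 × 14 = 11.9, so 12 days.
- 21/21: 0.85 × 21 = 17.85, so 18 days.

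Both match the protocol. The off-week is 7/21 = 33% of the DLT window.

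**2. The two definitions applied to the same cases** (a related, listed cycle 1 event):

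| Case | Protocol 3.2 / SAP 12.3 wording | Synopsis / event-type wording |
|---|---|---|
| 14/21, off-week event, reduced dose at restart | DLT (dose modification) | DLT |
| 14/21, off-week event, on-time restart at unchanged dose | Can be no DLT | DLT |
| Any schedule, evaluable patient, treatment ends with progression as the reason | Can be no DLT | DLT |
| Stop for progression before 12 (14/21) or 18 (21/21) days, no scored DLT | Not evaluable, replaced | DLT, therefore evaluable |

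The definitions part in the last three rows. Rows two and three are the ones in which a patient can be counted as DLT-free.

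A late restart is a further unclear case. SAP 12.2 defines an intra-cycle interruption as a zero dose between two non-zero doses, which an off-week event cannot produce within cycle 1. It leaves delay undefined, and SAP 12.3 does not name delay.

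**3. Patients on schedules with planned off-days** (SAP 6.1 column headers; 5-7 is read as 5 days on in each 7):
- Acute leukemia (AL), escalation: 3 + 3 + 4 + 4 + 8 + 7 + 7 = 36.
- Other hematologic malignancies (OHM), escalation: 3 + 5 + 5 = 13.
- Escalation total: 36 + 13 = 49.
- Expansion: 19 + 16 + 16 = 51, all on the RD schedule after the RD was set.

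At 80 mg QD 14/21 the escalation columns hold 4 AL patients and no OHM patients.

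**4. Sensitivity of the escalation rules (illustration only).** The documents give no target DLT rate or operating characteristics. Assume a true cycle 1 rate p of listed events and a fraction f not scored, so the counted rate is q = p(1 − f).
- P(escalate) = (1 − q)³ + 3q(1 − q)² × (1 − q)³
- P(at most 1/6) = (1 − q)⁶ + 6q(1 − q)⁵

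| p | f | q | P(escalate) | P(at most 1/6) |
|---|---|---|---|---|
| 0.33 | 0 | 0.330 | 0.434 | 0.358 |
| 0.33 | 0.1 | 0.297 | 0.500 | 0.427 |
| 0.33 | 0.2 | 0.264 | 0.570 | 0.501 |
| 0.33 | 1/3 | 0.220 | 0.665 | 0.606 |
| 0.25 | 0 | 0.250 | 0.600 | 0.534 |
| 0.25 | 1/3 | 0.167 | 0.780 | 0.737 |

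f = 1/3 is an upper illustration: onset uniform over 21 days and every off-week event missed.

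A milder assumption is that only 10% to 20% of off-week events go unscored because progression intervenes. Then f = 1/3 × 0.10 = 0.033 to 1/3 × 0.20 = 0.067. With p = 0.33, P(0/3) = (1 − q)³ moves from 0.30 to about 0.32 to 0.33.

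**The case against.** A reader might infer that a listed toxicity always needs a dosing change to count, so that every off-week event is lost and the RD schedule looks better tolerated than it is. On that view 100 of 141 patients are affected, and P(0/3) rises from 0.67³ = 0.30 to 0.78³ = 0.47 at p = 0.33. The documents do not support this reading:

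- **The condition is not uniform.** Both synopses and the fatigue sentence score by event type. Repeating the condition in the grade 2 item would be redundant if the opening sentence of 3.2 governed every item.
- **Off-week timing alone is not enough.** Protocol 5.2.4.2 lists the triggering events on their own terms and provides for a reduced dose on resumption, which is a dose modification under 3.2.
- **Progression can intervene on continuous dosing too.** A stop before the evaluability threshold leads to replacement, not to a DLT-free count.
- **AL patients have their own hematological rule** (marrow findings at day 22, confirmed at day 43). The grade 4 thrombocytopenia item applies only to OHM.
- **51 of the 100 patients are expansion patients.** Their DLTs did not drive escalation.
- **The 0.47 figure assumes every off-week event is missed.** The documents give no missed fraction.
- **There are safeguards.** The Safety Monitoring Committee (SMC) validates DLTs, suspected DLTs are reported as serious adverse events with a DLT box, and each adverse event record carries its own action taken.

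All of this stands, and it narrows the point. It does not remove it. No passage says how to score an event followed by an unchanged restart or by a stop for progression, and the SAP section that defines the primary analysis uses the wording that depends on dosing action.

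**Conclusion.** The point holds as a conflict between two definitions of the primary endpoint, with a narrow scoring gap under one of them. The gap is confined to listed events on planned off-days followed by an unchanged restart, and to listed events in DLT-evaluable patients whose treatment ends for progression. On intermittent schedules it concerns 49 escalation patients, plus 51 in expansion for the reported DLT counts only. How many events fall into the gap is unknown, and the probabilities above rest on assumed values of p and f. They show how sensitive the rules are and do not measure a bias. SAP 5 states that the study is complete, so rewording cannot change past escalation decisions. What it can change is how the DLT counts behind the RD are reported and read.

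**What to change.** **Reconcile the definition.** Bring the protocol synopsis, protocol 3.2, 3.2.1 and 5.2.4.2, the SAP synopsis and SAP 12.3 into line. One definition should state explicitly whether a listed cycle 1 event counts regardless of whether a dose was due or changed. Dosing rules need not be altered.

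**Add a sensitivity DLT table to SAP 12.3.** By dose level, score all related listed cycle 1 events by grade and duration whatever the dosing action. Flag those with onset on planned off-days and those in patients who stopped for progression by day 22. Use laboratory data as well as adverse event records, because protocol 7.3.2.2 keeps grade 3-4 laboratory changes without clinical consequences out of the adverse event pages. For those values, state how relationship to treatment will be judged.

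**Align the evaluability text at the same time.** Protocol 11.2 and SAP 8 give 18 full-dose days for all OHM patients, which a 14/21 schedule cannot reach. Protocol 3.1.1 sets the threshold by schedule.

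**Cost.** Wording changes and one additional table from data already collected. DLT counts at some dose levels may become slightly less favourable.
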